#### IV. STUDY DESIGN

This is a phase 2 study of E7070 in combination with idarubicin and cytarabine in patients with relapsed/refractory AML with a particular focus towards patients with primary refractory disease or who are receiving first salvage therapy or beyond. Patients with newly diagnosed AML who do not qualify for front-line induction studies will also be eligible. HRMDS patients will also be eligible. Patients will be treated according to the schedule below:

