## Protocol Body

E7070 Amendment 6 Final 11-15-2013.doc

**Title: A Phase 2, Open-label Study of E7070, Idarubicin and Cytarabine in Patients with Relapsed or Refractory Acute Myeloid Leukemia and High-Risk Myelodysplastic Syndromes.**

**Principal Investigator:** [name]

**Protocol Number:** 2009-0570

**Date of Protocol:** May 25, 2010

**Amendment #1:** February 9, 2011

**Amendment #2:** July 11, 2012

**Amendment #3:** October 3, 2012

**Amendment #4:** March 14, 2013

**Amendment #5:** June 21, 2013

**Amendment #6:** November 15, 2013

|                                       |   |
|---------------------------------------|---|
| TITLE                          | A Phase 2, Open-label Study of E7070, Idarubicin and Cytarabine in Patients with Relapsed or Refractory Acute Myeloid Leukemia and High-Risk Myelodysplastic Syndromes.  |
| INVESTIGATORS / TRIAL LOCATION | [name].
University of Texas M.D. Anderson Cancer Center
Dept. of Leukemia,
[name]
[name]  |
| SUPPORTER                      | Eisai, Inc.   |
| STUDY OBJECTIVES               | 
Primary objective:
 
 
1. To assess the complete response (CR) and CR with incomplete platelet recovery (CRp) rates with combination therapy of E7070, idarubicin and cytarabine in patients with relapsed or refractory acute myeloid leukemia (AML) or high-risk myelodysplastic syndromes (HRMDS)
 
2. To determine the safety and toxicity profile of combination therapy with combination therapy of E7070, idarubicin and cytarabine in patients with relapsed or refractory AML or HRMDS.
 
 
Secondary objectives:
To determine the:
 
 
1. duration of response;
 
2. disease-free survival; and
 
3. overall survival
 
  |
| STUDY DESIGN                   | Phase 2   |

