| STUDY POPULATION               | 
Eligibility criteria:
 Inclusion:
 
 
1. All patients with histologically or cytologically confirmed relapsed or refractory AML [except acute promyelocytic leukemia], or HRMDS (Int-2 high risk by IPSS or >10% blasts in marrow).
 
2. Patients must be 18 years or older.
 
3. Patients must have a performance status of 0-2 (Zubrod scale).
 
4. Patients must have adequate renal function (serum creatinine <math>\leq</math> 1.3 mg/dL and/or creatinine clearance <math>></math> 40 mL/min). Patients with renal dysfunction due to organ infiltration by disease may be eligible after discussion with the P.I., (up to creatinine <math>\leq</math> 2.0) and appropriate dose adjustments will be considered.
 
5. Patients must have adequate hepatic function (bilirubin <math>\leq</math> 2.0 mg/dl; SGOT or SGPT <math>\leq</math> 3X the ULN for the reference lab unless due to leukemia or congenital hemolytic disorder or bilirubin) excretion disorder. Patients with hepatic dysfunction (SGOT/SGPT up to <math>\leq</math> 5X ULN) due to organ infiltration by disease may be eligible after discussion with the P.I., and appropriate dose adjustments will be considered.
 
6. Patients must have normal cardiac ejection fraction.
 
7. QTc interval <math>\leq</math> 480 msec.
 
8. Patients must sign an informed consent form indicating that they are aware of the investigational nature of this study, in
 
 |

|  |   |
|--|---|

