## I. OBJECTIVES

### Primary Objectives

1. To assess the complete response (CR) and CR with incomplete platelet recovery (CRp) rates with combination therapy of E7070, idarubicin and cytarabine in patients with relapsed or refractory acute myeloid leukemia (AML) or high-risk myelodysplastic syndromes (HRMDS), and.
2. To determine the safety and toxicity profile of combination therapy with combination therapy of E7070, idarubicin and cytarabine in patients with relapsed or refractory AML or HRMDS.

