## II. BACKGROUND

### *The Disease*

The cure rates for patients with relapsed or refractory hematological malignancies are dismal. Therefore, new agents need to be identified, tested in clinical trials, and incorporated into effective regimens to improve the prognosis of these patients. This study is designed for patients with relapsed/refractory AML and HRMDS whose duration of first CR was less than 1 year. Once front-line therapy fails, patients' therapeutic options are limited. This population of patients with disease that has relapsed or is refractory to established frontline therapies has response rates of less than 10% to 20%. Even if a small proportion of these patients achieve a remission, the remissions are short lasting.

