### *Rationale for Proposed Therapy*

#### **Idarubicin and Cytarabine**

While a combination of an anthracycline (daunorubicin or idarubicin) and cytarabine is standard 'induction' regimen for patients with newly diagnosed AML, the 'best' salvage regimen for patients with relapsed disease is unclear. While patients with initial CR duration of over 1 year clearly benefit from high-dose cytarabine (HDAC) based regimens, the probability of achieving a second CR for patients with shorter first CR duration is very low. Cytogenetics, age, failure of prior salvage attempts add to the poor outcome of these patients. Investigational agents alone or in combination with traditional chemotherapy in clinical trials should be the most appropriate approach for these patients.

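### Section IV admits newly diagnosed AML, but the title, objectives and Inclusion 1 do not, and Section XX does not say which patients its 10% null and response counts cover

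*Combined protocol and SAP*

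**What the plan says.** Four places define the population one way. The title reads "in Patients with Relapsed or Refractory Acute Myeloid Leukemia and High-Risk Myelodysplastic Syndromes". Both primary objectives, in the synopsis and in Section I, name the same two groups. Inclusion 1, identical on this point in the synopsis and in Section V, reads "All patients with histologically or cytologically confirmed relapsed or refractory AML [except acute promyelocytic leukemia], or HRMDS". None of the remaining inclusion or exclusion criteria admits newly diagnosed AML.

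Section IV (Study Design) goes further. It first describes relapsed or refractory AML with a focus on "primary refractory disease or who are receiving first salvage therapy or beyond", then adds: "Patients with newly diagnosed AML who do not qualify for front-line induction studies will also be eligible". High-risk MDS is admitted in a separate sentence, so newly diagnosed AML is a distinct third group.

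Section XX speaks only of leukemia patients. It applies a Simon minimax design with a null of 10% and a target of 25%: stop if 2 or fewer of 27 respond, and conclude ineffective if 6 or fewer of 40 respond. It sets no stratum or cap and defines no analysis population. It does not say whom the 10% describes or where it comes from. The only historical rate is in Section II (The Disease), which says that "disease that has relapsed or is refractory to established frontline therapies has response rates of less than 10% to 20" percent.

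**The concern.** A patient with newly diagnosed AML is eligible under Section IV and fails Inclusion 1 under Section V. Depending on which section is followed, that patient is either refused, or enrolled and counted while outside the primary objective.

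This matters for the analysis because the trial has one arm. The fixed 10% is the only comparator, so a pass or fail can be interpreted only when it is clear which patients the 10% is meant for. If patients from outside that population enter the counts, the stated error rates describe a different group from the one observed.

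**Working it through.** **1. The texts side by side.**

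| Place | Relapsed/refractory AML | High-risk MDS | Newly diagnosed AML |
|---|---|---|---|
| Title | yes | yes | not named |
| Primary objectives (synopsis, Section I) | yes | yes | not named |
| Inclusion 1 (synopsis, Section V) | yes | yes | not admitted |
| Section IV | yes | yes | eligible |
| Section XX | leukemia patients, no stage given | not named | not named |
| Historical rate, Section II | yes | not separated | not covered |

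The conflict is in current text. It does not come from an amendment summary or from a gap in the document.

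**2. The plan's own figures.** Inputs from Section XX: n1 = 27, r1 = 2, n = 40 (13 more in stage 2), r = 6, null 0.10, target 0.25, significance level 0.1, power 90%, early termination 0.48. With response rate p:

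- Early stop = P(X1 ≤ 2), X1 ~ Bin(27, p).
- Pass = sum over x = 3 to 27 of P(X1 = x) × P(X2 ≥ 7 − x), X2 ~ Bin(13, p).

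At p = 0.10, early stop = 0.9^27 + 27(0.1)(0.9^26) + 351(0.01)(0.9^25) = 0.0581 + 0.1744 + 0.2520 = 0.485 to three places, against 0.48 stated. The pass probability is 0.0977 at p = 0.10 (type I error) and 0.9001 at p = 0.25 (power). A search over all two-stage designs confirms that this is the minimax design. The arithmetic of Section XX is right.

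**3. Sensitivity to the background rate of the patients counted.** These rates are assumptions; the documents give none by subgroup. Each row applies the same formulas to a treatment that adds nothing.

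| Background rate | Early stop | Pass |
|---|---|---|
| 8% | 0.63 | 0.04 |
| 10% (null) | 0.48 | 0.098 |
| 12% | 0.36 | 0.19 |
| 14% | 0.25 | 0.32 |
| 16% | 0.17 | 0.46 |

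**4. How a mix could produce such rates.** Suppose 8 of 40 patients are newly diagnosed (5 in stage 1, 3 in stage 2) and the other 32 respond at 10%. If the newly diagnosed respond at 20%, 30% or 40%, the pooled rate is 0.8 × 10% + 0.2 × 20% = 12%, or likewise 14% or 16%. Keeping the two groups as separate binomials, the pass probabilities are 0.193, 0.317 and 0.459. If they also respond at 10%, nothing changes.

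**5. Mixes can cancel.** With 32 patients at 8% and 8 at 18%, the pooled rate is 0.8 × 8% + 0.2 × 18% = 6.4% + 3.6% = 10%. A simulation with these patients in random order (400,000 runs) gave pass 0.096 and early stop 0.485, essentially the nominal values.

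**The case against.** **Section V would govern in practice.** An inclusion list is where screening staff would look, and perhaps no newly diagnosed patient would enrol. That is possible, but no precedence rule is stated and Section IV grants eligibility outright. The texts conflict even if the number enrolled is zero.

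**The population and source of the 10% can be inferred.** This largely stands for relapsed or refractory disease. The title and objectives name the population, and Section II gives a cited range that could be the unstated basis. For those patients the gap is a missing cross-reference. Two cautions remain. The Section II range can be read in more than one way, and that section does not define response, whereas Section XX counts CR, CRp, PR and marrow clearance together. In no reading does the range cover newly diagnosed AML.

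**The 10% is a decision threshold.** Section XX uses it as the rate at or below which the treatment is not worth pursuing, so it need not equal every subgroup's background rate. That is fair. It must still suit the patients counted, and the plan does not say who they are.

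**A stronger reading is tempting.** A reader might infer that admitting newly diagnosed patients inflates the false-positive rate. The documents do not support this. They give no share, response rate or prognosis for these patients, and those not qualifying for front-line studies could do better or worse than the rest. The table in the working shows sensitivity, not demonstrated harm.

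**Conclusion.** The contradiction stands with high confidence: Section IV admits a group that the title, objectives and Inclusion 1 leave out, and Section XX does not say whether that group enters the 2/27 and 6/40 counts. The only historical rate in the documents cannot justify a 10% null for newly diagnosed AML.

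The consequence is not quantified. At its own inputs the design holds (0.098, 0.900, 0.485). Under assumed background rates of 8% to 16%, the chance of passing without added benefit runs from 0.04 to 0.46, so the rule is sensitive to who is counted. Neither the direction nor the size of any shift can be derived from the documents. This should be fixed, but it is no evidence that the sample size or boundaries are wrong.

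One secondary point: Section II says "This study is designed for patients with relapsed/refractory AML and HRMDS whose duration of first CR was less than 1 year". A reader might take this as a second eligibility conflict. It is background narrative, and primary refractory patients have no first remission to time, so it is only wording that could be aligned with Inclusion 1.

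**What to change.** 1. Reconcile the title, synopsis, Sections I, IV and V into one eligibility statement. Which population to study is the sponsor's choice.
2. Add to Section XX, for example: *The 10% null and the 2/27 and 6/40 efficacy counts refer to the population of the primary objective. Membership is determined from baseline records without reference to response. The 10% is based on [source], for the response definition used here.*
3. If newly diagnosed AML stays eligible, choose one of two routes and write it down:
   - Report these patients separately, outside the 27 and 40 efficacy counts. State whether the synopsis ceiling of 40 rises, since otherwise fewer than 40 patients would remain for the 6/40 rule. State also which patients form the denominator of the toxicity boundaries, which are listed only up to 16/40.
   - Count them, justify a null for the mixed population and recompute the two-stage design.
4. Optionally, align the first-remission wording in Section II with Inclusion 1.

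The cost is wording in the affected sections. Accrual may be slower if the narrower population is chosen, and the total may need revision if newly diagnosed patients are kept.

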##### A. Treatment Plan

[figure not shown]
E7070 400 mg/m^2 intravenously (IV) approximately over 1 hour on day 1 and day 8 (± 2 days on Day 8 only) followed by:

- Idarubicin 8 mg/m^2 IV approximately over 1 hour daily x 3 (days 9-11) and
- Cytarabine 1.0 g/m^2 IV approximately over 24 hours daily on day 9-12 (age <60 years) or days 9-11 (age ≥ 60 years).
- Dexamethasone 10 mg IV daily for 3-4 days with cytarabine

Variations in infusion times due to minor differences in IV bag overfill/underfill and institutional procedure on flushing chemotherapy lines will not result in protocol deviation.

Patient will undergo disease assessment on day 28 ± 3 days at the discretion of treating physician. This assessment can be repeated or delayed at the discretion of treating physician if there is ground to believe that the patient is benefiting from study drug. Patients who derive clinical benefit e.g. CR, CRp, PR or marrow clearance of blasts may receive up to two additional cycles of E7070 in combination with chemotherapy at the above doses. Each cycle will be approximately 28 days (+/- 2 days). Dose modifications and delays are allowed for persistent cytopenias or non-hematological toxicities.

Patients not achieving less than an objective response after cycle 1 may receive another cycle of therapy if considered to be in best interest by investigator. If such a patient achieves an objective response as defined in response criteria after the second cycle may receive one more cycle of therapy on study. If a patient does not achieve an objective response after two cycles of therapy, the patient will be removed from study for lack of response.

**B. Dose modification** will be according to Table 1:

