## **VIII. EVALUATION DURING STUDY**

- CBC, differential (if WBC >  $10^9/L$ ), every 4-7 days during Cycle 1 and every 1 to 4 weeks during Cycle 2.
- Record all concomitant medications and adverse events: continuously during study.
- Disease assessment: Cycle 1, Day 28 (+/- 3 days)
- Electrocardiogram on Day 2 (+/- 1 day) and Day 8 (+/- 2 days) of Cycle 1 done at least 1 hour after completion of E7070 infusion.
- Bone marrow aspiration on day 28 (+/- 3 days) and as indicated at the discretion of the treating physician until documentation of response. Bone marrow examinations may be omitted in patients where there is clear evidence of active disease (e.g., increasing blasts in peripheral blood).
- Creatinine, total bilirubin, electrolytes, AST and/or ALT once every week during induction Cycle 1, then every 2-4 weeks during Cycle 2.
- Safety lab assessments (CBC, differential, platelets, creatinine, total bilirubin, electrolytes, AST and/or ALT) can be performed by local physician, see Section X.

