## **IX. END-OF-TREATMENT VISIT (30 days [+/- 5 days] after the last dose of study drug), unless the patient has started on alternative therapy**

- CBC, platelet count, differential
- Serum chemistries (creatinine, total bilirubin, electrolytes, AST and/or ALT)
- Record adverse events

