 To include glucose, total protein, albumin, electrolytes [sodium, potassium, chloride, CO2], calcium, phosphorus, magnesium, uric acid, bilirubin (total, direct), SGPT (ALT) or SGOT (AST), alkaline phosphatase, lactate dehydrogenase, creatinine, blood urea nitrogen will be performed at least weekly.

 Creatinine, total bilirubin, electrolytes, AST and/or ALT once every week during Cycle 1, then every 2-4 weeks during Cycles 2-3.

 Within one month, to include cytogenetics, unless these tests were done within 3 months.

 And as indicated until documentation of response. Bone marrow examinations may be omitted in patients where there is clear evidence of active disease (e.g., increasing blasts in peripheral blood)

 At or within 1 month of screening

 Done at least 1 hour after completion of E7070 infusion if EKG is done on the day of the E7070 infusion day

 For women of childbearing potential within 7 days prior to day 1

 If patient is found to be CR, CRp, PR or marrow clearance of blasts, may receive up to 2 additional cycles of E7070 in combination with chemotherapy

 To include vital signs and weight

 Approximately every 28 days to 2 additional cycles

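### Does the first-cycle response rate need a written last counting day, given that the day-28 assessment may be repeated or delayed?

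*Combined protocol and SAP*

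**What the plan says.** Section XX (Statistical Considerations) measures efficacy by CR, CRp, PR or marrow clearance in the first cycle. It applies a Simon minimax rule to that count: stop at 2 or fewer responders of 27, and conclude ineffective at 6 or fewer of 40. Section I makes the CR and CRp rates the first primary objective.

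On timing, Section IV.A (Treatment Plan) says: "Patient will undergo disease assessment on day 28 ± 3 days at the discretion of treating physician". It goes on: "This assessment can be repeated or delayed at the discretion of treating physician if there is ground to believe that the patient is benefiting" from the study drug. On cycle length it says "Each cycle will be approximately 28 days (+/- 2 days"), and adds that "delays are allowed for persistent cytopenias or non-hematological toxicities", with no maximum.

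Section VIII (Evaluation During Study) lists the disease assessment under Cycle 1. After the day-28 marrow it allows further marrows "as indicated at the discretion of the treating physician until documentation of response". Footnote 6 of Section XII (Schedule of Assessments) agrees: "And as indicated until documentation of response". Both let the marrow be omitted when disease is clearly active.

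Blood counts have their own schedule in Section VIII, "every 4-7 days during Cycle 1 and every 1 to 4 weeks during Cycle 2". Section IX adds an end-of-treatment count 30 ± 5 days "after the last dose of study drug), unless the patient has started on alternative therapy".

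**The concern.** The only dated marrow on treatment is the day 28 ± 3 one. Later looks are discretionary, and in Section IV.A they are tied to the physician's belief that the patient is doing well. No sentence says until when a response from such a look counts as first-cycle response.

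Take a patient not yet re-treated whose marrow is delayed to day 38, or whose neutrophils recover a week after a cleared day-28 marrow. That patient could be scored either way, and the choice could be made with the result in view. With treatment known to everyone and no control arm, nothing in the design would cancel the effect.

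The CR/CRp rate is the more exposed quantity, because under Section XIII both categories need a neutrophil count of at least 1.0 × 10⁹/L. The two-stage boundaries are also tight enough that a single reclassified patient can change the decision.

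**Working it through.** **1. The stated design.** Inputs from Section XX: p0 = 0.10, p1 = 0.25, n1 = 27, r1 = 2, n = 40, r = 6.

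- Early stopping = P(X1 ≤ 2 | 27, 0.10) = 0.4846 (stated 0.48).
- P(promising | p) = Σ over x1 ≥ 3 of P(X1 = x1 | 27, p) × P(X2 ≥ 7 − x1 | 13, p).
- At p = 0.10 this is 0.0977 (stated limit 0.1). At p = 0.25 it is 0.9001 (stated 90%).

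The design is in order. The question is only what is counted.

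**2. Which cases the text already settles.**

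- *Look on day 31.* The assessment window is 28 − 3 = 25 to 28 + 3 = 31, and the nominal cycle is 28 − 2 = 26 to 28 + 2 = 30. The one-day overhang is not a conflict. Sections VIII and XII assign the look to Cycle 1, and the cycle length is approximate.
- *Response first reached in Cycle 2.* It is outside the first-cycle frame of Section XX. Section IV.A likewise separates the outcome after one cycle from the outcome after two.
- *Cleared marrow near day 28, counts still low.* It already scores in the composite as marrow clearance. This assumes that the term covers marrow CR (MDS) and morphologic leukemia-free state (AML) in Section XIII; the latter disregards counts.
- *Marrow uncleared, delayed or not done, Cycle 2 not started.* This is the only group open to a later call on the composite.
- *CR/CRp with late count recovery.* Open, but count data exist. For a patient treated for one cycle, the end-of-treatment count falls between 8 + 25 = day 33 (from the last E7070 dose) and 12 + 35 = day 47 (from the last cytarabine dose under age 60).

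**3. Sensitivity of the composite to one call, if one occurred in stage 1 of every trial.**

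- One response added (effective boundaries 1/27 and 5/40): P(promising | 0.10) = 0.205.
- One left out (effective boundaries 3/27 and 7/40): P(promising | 0.25) = 0.807.

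If such a call arose in a share s of trials (s is assumed; the documents give none):

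- s = 10%: 0.9 × 0.0977 + 0.1 × 0.2051 = 0.108; 0.9 × 0.9001 + 0.1 × 0.8072 = 0.891.
- s = 25%: 0.75 × 0.0977 + 0.25 × 0.2051 = 0.125; 0.75 × 0.9001 + 0.25 × 0.8072 = 0.877.

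The added-response figures are a type I error only if the 10% benchmark refers to a day-28 look, which the documents do not say. All of these figures describe how tight the boundaries are. None estimates a bias.

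**4. CR/CRp rate.** One patient is 1/40 = 2.5 points. Two patients, with 6 and 8 assumed as counts, move the rate from 6/40 = 15.0% (exact 95% CI 5.7 to 29.8) to 8/40 = 20.0% (9.1 to 35.7). The shift is 5 points against an interval 29.8 − 5.7 = 24.1 points wide.

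**The case for a change.** The strongest case for a change is that the disputed patient is a plausible one. Idarubicin starts on day 9, and Section III.C gives marrow recovery at 21 to 28 days without a starting point. Counted from the first dose (an assumption), that is days 30 to 37, mostly beyond the day-31 end of the scheduled window. At a true rate of 10% the chance of exactly 2 responders of 27 is 0.25, so a trial sitting on the interim boundary is no rarity. The confidence-interval sentence in Section XX names no cycle and omits marrow clearance, so that rate lacks the protection the composite has. One sentence would close the gap at almost no cost.

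Part of this stands: no last day is written, and writing one would be tidier. The rest is weaker.

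- The recovery figures are generic and not specific to this regimen. They show that the case can arise, not how often.
- Sections VIII and XII allow further marrows as indicated, so later looks do not depend on perceived benefit alone.
- Section XIII takes response from the International Working Group criteria. Whether those settle how marrow and counts are paired cannot be checked from the documents, so a missing pairing rule cannot be asserted.
- The CR/CRp rate and the interval estimate carry no decision boundary.
- A cut-off has its own costs. Day 42, or day 47 to take in every end-of-treatment count, appears nowhere in the documents. Either would lengthen ascertainment by 42 − 31 = 11 or 47 − 31 = 16 days against unchanged boundaries. Repeat marrows would stay discretionary, and a patient starting Cycle 2 near day 28 would still have a shorter window.

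**Conclusion.** No change to the plan follows. What is missing is a last calendar day for a patient who has not begun Cycle 2, and the existing text points to a sensible reading: best response documented before Cycle 2 or other anti-leukemia therapy. Analysts would adopt that and state it in the report. A fixed cut-off day is a debatable alternative that would leave the discretionary looks in place.

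The size and direction of any effect cannot be determined from the documents. The decision rule is largely protected because marrow clearance counts, on the assumption that it includes a cleared marrow without count recovery. For CR/CRp the scale is 2.5 points per patient, small beside an interval some 24 points wide at 6/40. The conclusion also assumes that the first-cycle frame is read plainly, so that responses first seen after Cycle 2 begins are left out of the 2/27 and 6/40 counts.
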